## 2.8.1 Analysis of adverse events

### 2.8.1.1 Definitions

Adverse event observation period:

- Pretreatment adverse events are adverse events that developed or worsened or became serious from the signed informed consent date up to the first administration of IMP.
- TEAEs are adverse events that developed or worsened or became serious during the TEAE period.
- Posttreatment adverse events are adverse events that developed or worsened or became serious during the posttreatment period.

All AEs (including serious adverse events and adverse events of special interests) will be coded with a lower-level term (LLT), PT, high-level term (HLT), high-level group term (HLGT), and associated primary SOC using the version of MedDRA currently in effect at Sanofi at the time of database lock.

Adverse events of special interest (AESI) and other selected AE groupings will be searched based on the criteria detailed in [Table 6](#).

**Table 6 - Criteria for adverse events of special interest and other selected AE groupings**

AE Grouping	Criteria
AESI	
Anaphylactic reaction	Anaphylactic reaction algorithmic approach ( Introductory Guide for Standardised MedDRA Queries (SMQs) Version 18.1 ): includes anaphylactic reaction narrow SMQ (20000021) terms; for selection based on occurrence of multiple events, the events must have occurred within 24 hours of each other
Hypersensitivity (medically reviewed)	SMQ hypersensitivity (20000214) narrow search and [AE corrective treatment/therapy='Y' or Action taken with IMP='Drug withdrawn' or Action taken with IMP='Drug interrupted'] followed by blinded medical review (documented process) for selection of relevant events
Serious injection site reactions or severe injection site reactions that last longer than 24 hours	HLT = 'Injection site reaction' and either with serious status, or with severe status and (AE end date/time - AE start date/time) ≥ 24 hours or ongoing
Severe or serious infection	Primary SOC = 'Infections and infestations' and with severe or serious status
Parasitic infection	Infection Type 'Parasitic' checked on eCRF Infection Defined as AESI Complementary Form
Opportunistic infection	Infection Type 'Opportunistic' checked on eCRF Infection Defined as AESI Complementary Form
Drug-related hepatic disorder	Drug-related hepatic disorders-Comprehensive search narrow SMQ (20000006)
Pregnancy	Primary SOC = 'Pregnancy, puerperium and perinatal conditions' or PT in (Aborted pregnancy, False negative pregnancy test, Pregnancy test positive, Pregnancy test urine positive, Ectopic pregnancy termination)
Symptomatic overdose with IMP	Is the event a Symptomatic Overdose with IMP? is answered Yes on AE eCRF.
Symptomatic overdose with non-IMP	Is the event a Symptomatic Overdose with non-IMP? is answered Yes on AE eCRF
Other selected AE grouping	
Injection site reaction	HLT = 'Injection site reaction'
Malignancy	Sub-SMQ (20000091)– Malignant or unspecified tumors
Suicidal behavior	PT in (Completed suicide, Suicidal ideation, Depression suicidal, Suicidal behavior, Suicide attempt)
Partner pregnancy	PT in (Pregnancy of partner, Miscarriage of partner)
Conjunctivitis (narrow)	PT in (Conjunctivitis, Conjunctivitis allergic, Conjunctivitis bacterial, Conjunctivitis viral, Atopic keratoconjunctivitis)
Conjunctivitis (broad)	PT in (Conjunctivitis, Conjunctivitis allergic, Conjunctivitis bacterial, Conjunctivitis viral, Atopic keratoconjunctivitis, Blepharitis, Dry eye, Eye irritation, Eye pruritus, Lacrimation increased, Eye discharge, Foreign body sensation in eyes, Photophobia, Xerophthalmia, Ocular hyperaemia, Conjunctival hyperaemia)
Eosinophilia	HLT = 'Eosinophilic disorders' or PT = 'Eosinophil count increased'

### **2.8.1.2 General information**

The primary focus of adverse event reporting will be on TEAEs. Pretreatment adverse events will be described separately.

If an adverse event date/time of onset (occurrence, worsening, or becoming serious) is incomplete, an imputation algorithm will be used to classify the adverse event as pretreatment or treatment-emergent. The algorithm for imputing date/time of onset will be conservative and will classify an adverse event as treatment emergent unless there is definitive information to determine it is pretreatment. Details on classification of adverse events with missing or partial onset dates are provided in [Section 2.11.5](#).

Multiple occurrences of the same event in the same patient will be counted only once in the tables within a treatment phase. The denominator for computation of percentages is the safety population within each treatment group. Sorting will be based on results for the dupilumab group.

### **2.8.1.3 Treatment-emergent adverse events**

The following treatment-emergent adverse event summaries will be generated for the safety population.

- Overview of TEAEs, summarizing number (%) of patients with any
  - Treatment-emergent adverse event.
  - Serious treatment-emergent adverse event.
  - Treatment-emergent adverse event leading to death.
  - Treatment-emergent adverse event leading to permanent treatment discontinuation.
- All TEAEs by primary SOC, showing number (%) of patients with at least 1 TEAE, sorted by internationally agreed order of primary SOC.
- Number (%) of patients experiencing TEAE(s) presented by PT, sorted by decreasing incidence of PT.
- All TEAEs by primary SOC and PT, showing the number (%) of patients with at least 1 TEAE, sorted by the internationally agreed SOC order and by decreasing incidence of PTs within each SOC.
- All TEAEs by maximal intensity, presented by primary SOC and PT, showing the number (%) of patients with at least 1 TEAE by severity (i.e., mild, moderate, or severe), sorted by the internationally agreed SOC order and by decreasing incidence of PTs within each SOC.
- All TEAEs regardless of relationship and related to IMP by primary SOC and PT, showing the number (%) of patients with at least 1 TEAE, sorted by the internationally agreed SOC order and by decreasing incidence of PTs within each SOC.
- A listing of all treatment-emergent adverse events will be presented.

#### **2.8.1.4 Treatment-emergent adverse event(s) leading to permanent treatment discontinuation or drug interruption**

A listing of all treatment-emergent adverse events leading to permanent treatment discontinuation or drug interruption will be presented

#### **2.8.1.5 Adverse events of special interests and other selected AE groupings**

- All AESIs by selected standardized MedDRA query (SMQ) and PT or by laboratory values (as in ALT elevation), showing the number (%) of patients with at least 1 PT, sorted by decreasing incidence of PTs within each SMQ
- For each pre-specified AESI and selected AE grouping,
  - Number (%) of patients with any specific TEAE.
  - Number (%) of patients with any specific serious AE (regardless of treatment emergent status).
  - Number (%) of patients with any specific treatment emergent serious AE.
  - Number (%) of patients with any specific AE leading to death.
  - Number (%) of patients with any specific TEAE leading to permanent study drug discontinuation.
  - Number (%) of patients with any specific TEAE by maximum intensity, corrective treatment, and final outcome.
  - Number (%) of patients with any specific TEAE regardless of relationship and related to IMP.
  - All of the specific TEAE, by PT, showing the number (%) of patients, sorted by decreasing incidence of PT.
- Number (%) of patients with injection site reactions by the related injection.
- Number (%) of patients with different numbers of injection site reactions.
- A listing of the AEs will be presented.

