### **1.1 STUDY DESIGN AND RANDOMIZATION**

PDY14192 is a Phase 2a, exploratory, multinational, multicenter, randomized, double-blind, placebo-controlled, parallel group study of repeated doses of dupilumab or placebo administered subcutaneously (SC) every 2 weeks (q2w) for 12 weeks in adult patients with persistent asthma who are receiving at minimum a medium to high dose of inhaled corticosteroid (ICS) in combination with long-acting beta-agonists (LABA). Patients requiring a third asthma controller are eligible. Both the patients and investigators will be blinded to assigned active drug or matching placebo.

After a screening phase of up to 6 weeks (5 weeks and optional addition of 7 days), patients will be centrally randomized (using allocation from block randomization schedule) via Interactive Voice Response System/Interactive Web Response System (IVRS/IWRS) in a 1:1 randomization ratio to dupilumab 300 mg q2w in 2 mL or placebo q2w in 2 mL. Randomization will be stratified by ICS dose level (medium, high) and region (North America, Europe).

During the study, patients will undergo 2 bronchoscopy procedures (one prior to the initiation of study drug and the other after 12 weeks of treatment) for the collection of bronchial biopsy, bronchial brushing and bronchoalveolar lavage fluid samples.

Approximately 42 patients will be randomized to dupilumab or placebo (around 21 patients per group) with at least 21 patients receiving treatment with high dose of ICS and no more than 8 patients with baseline blood eosinophils < 150 cells/ $\mu$ L (i.e., 0.15 Giga/L).

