## 1.4 STUDY PLAN

The clinical trial consists of three periods:

- **Screening Period** (5 weeks and potentially additional up to 7 days): to determine a patient's eligibility status or scheduling of bronchoscopy and establish the level of asthma control before randomization. During the screening period, a bronchoscopy procedure is performed to acquire baseline samples.
- **Randomized Treatment Period** (12 weeks and potentially additional up to 4 weeks in the case the bronchoscopy at week 12 has to be postponed to week 14 or 16): to treat with dupilumab or placebo SC injection.
- **Post-treatment Period** (12 weeks): to monitor patients' statuses when off study drug treatment for patients not participating in the open label extension (OLE) LTS12551 study. Eligible patients participating in the OLE study will enter the study after completion of the EOT visit assessments. The post-treatment analyses for patients who enter the OLE study will be described in a separate SAP.

Figure 1 - Graphical study design

\*R: Randomization 1:1  
BC: Bronchoscopy  
IMP: Investigational Medicinal Product administration  
EOT: End-Of-Treatment visit  
EOS: End-Of-Study visit  
Visit windows for visits after Day 1 are +/- 3 days  
\*\*If a patient is unable to undergo a bronchoscopy at Week 12, the EOT visit may be postponed and up to 2 additional doses of IMP may be administered.

Refer to the [Appendix A](#) for the detailed study flow chart.

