## 2 STATISTICAL AND ANALYTICAL PROCEDURE

### 2.1 PATIENT DESCRIPTION

#### 2.1.1 Disposition of patients

This section describes patient disposition for patient study status.

Screened patients are defined as any patient who signed the informed consent.

Randomized patients consist of all patients with a treatment kit number allocated and recorded in the IVRS/IWRS database, and regardless of whether the treatment kit was used or not.

For patient study status, the total number of patients in each of the following categories will be presented in the Clinical Study Report (CSR) summary table (number and percentage):

- Screened patients.
- Screened failure patients and reasons for screen failure.
- Nonrandomized but treated patients.
- Randomized patients.
- Randomized but not treated patients and reason for not being treated.
- Randomized and treated patients.
- Patient who completed the 12-week treatment period as per protocol.
- Patients who did not complete the 12-week treatment period by main reason for permanent treatment discontinuation.
- Patients who did not complete the 12-week treatment period per patient's decision.
- Patients who completed the study as per protocol.
- Patients who withdraw from the study by main reason for study discontinuation.
- Patients who withdraw from the study per patient's decision.
- Patients who entered the LTS12551 study (OLE).
- Patients who did not continue into the LTS12551 study.
- Patients' status (alive, dead) at last study contact for patients who did not enter the LTS12551 study.

For all categories of patients (except for the screened categories and nonrandomized categories) percentages will be calculated using the number of randomized patients as denominator. This summary will be provided by treatment group and may also be further subgrouped by region and/or ICS dose as applicable.

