### **2.2.3 Safety population**

The safety population will consist of all patients randomized and exposed to IMP, regardless of the amount of treatment administered. Patients treated without being randomized will be included in the safety population. The patients for whom it is unclear whether they took the study medication will be included in the safety population.

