### ***General common rules related to PCSA for clinical laboratory evaluations, vital signs, and ECG***

- The potentially clinically significant abnormality (PCSA) values are defined as abnormal values considered medically important by the Sponsor according to predefined criteria/thresholds based on literature review and defined by the Sponsor for clinical laboratory tests, vital signs, and ECG ([Appendix F](#)).
- PCSA criteria will determine which patients has at least 1 PCSA during the treatment-emergent adverse event period, taking into account all evaluations performed during the treatment-emergent adverse event period, including nonscheduled or repeated evaluations. The number of all such patients will be the numerator for the on-treatment PCSA percentage.
- The treatment-emergent PCSA denominator by group for a given parameter will be based on the number of patients assessed for that given parameter in the treatment-emergent adverse event period by treatment group on the safety population. Number (%) of patients with at least 1 PCSA will be summarized regardless of baseline PCSA status and also by baseline PCSA status.
- For quantitative safety parameters based on central laboratory/reading measurements, descriptive statistics will be used to summarize results and change from baseline values by visit and treatment group.

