#### 2.11.5 Missing data

For categorical variables, patients with missing data are not included in calculations of percentages unless otherwise specified. When relevant, the number of patients with missing data is presented.

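### The by-injection table of injection site reactions has no denominator of its own, so the general adverse-event rule counts patients never given an injection as non-reactors to it

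*SAP*

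**What the plan says.** SAP section 2.8.1.5 lists, among the summaries of selected adverse-event groupings, "Number (%) of patients with injection site reactions by the related injection". The bullet does not say what the percentage is divided by.

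The rule for the adverse-event section is in 2.8.1.2: "The denominator for computation of percentages is the safety population within each treatment group". Neither section exempts the by-injection table. Section 2.2.3 defines the population: "The safety population will consist of all patients randomized and exposed to IMP, regardless of the amount of treatment administered". One injection is therefore enough to be in the denominator of every row.

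The SAP expects the number of recipients to vary by injection. Section 2.1.1 will tabulate "Patients who did not complete the 12-week treatment period by main reason for permanent treatment discontinuation". The study-design figure note in section 1.4 says that, when the Week 12 bronchoscopy cannot be done, "the EOT visit may be postponed and up to 2 additional doses of IMP may be administered".

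Elsewhere the SAP does state a narrower denominator. In section 2.8, the percentage denominator for potentially clinically significant abnormalities "will be based on the number of patients assessed for that given parameter in the treatment-emergent adverse event period".

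**The concern.** Only a patient who received injection k can react to injection k. Dividing by everyone who had at least one injection adds patients who were not at risk in that row and treats them as having tolerated the injection.

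A table by injection is naturally read down its rows, as local tolerability over successive administrations. Under the current rule, part of any decline may reflect only that fewer patients were injected. Tolerability compared with placebo is a stated objective (section 1.2.2), and injection site reaction is a prespecified grouping (Table 6).

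The planned summaries do not let a reader undo the effect. Exposure is summarised as duration (2.4.1), compliance as a percentage (2.4.2) and disposition as completers and non-completers (2.1.1). None of these gives the number of recipients of each injection.

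**Working it through.** **The plan's own figure.** The only computed design figure that bears on this point is the group size. Section 1.3 assumes a FeNO difference of 25 ppb, SD 32 ppb, a one-sided 5% t-test and 21 completers per group, and states 80% power. The effect size is 25/32 = 0.781, with 40 degrees of freedom and noncentrality 0.781 × √(21/2) = 2.53. The noncentral t distribution gives power 0.8005, so the figure reproduces. The concern does not depend on the power. It uses only N = 21, which is also the approximate number randomised per group in section 1.1.

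**Which rule applies.** There are two candidates.
- Section 2.8.1.2 sets the safety population of the group as denominator for adverse-event percentages.
- Section 2.11.5 says: "For categorical variables, patients with missing data are not included in calculations of percentages unless otherwise specified". It does not help. A patient who was never given an injection has no missing reaction record for it, and 2.8.1.2 does specify the adverse-event denominator.

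**Formula.** Let x_k be the patients reacting to injection k, n_k the patients who received it, and N the safety population of the group.
- Printed rate = x_k/N
- Rate among recipients = x_k/n_k
- Printed rate = (rate among recipients) × n_k/N
- Relative understatement = 1 − n_k/N

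Because n_k cannot exceed N, the printed rate is never too high.

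**Numbers.** N = 21. Every n_k below is an assumption. One reaction prints as 1/21 = 4.8% in every row.

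| Row | Assumed n_k | n_k/21 | Understatement | One reaction among recipients |
|---|---|---|---|---|
| First injection | 21 | 1.00 | 0% | 4.8% |
| Late scheduled | 20 | 0.95 | 5% | 5.0% |
| Late scheduled | 18 | 0.86 | 14% | 5.6% |
| Late scheduled | 17 | 0.81 | 19% | 5.9% |
| Optional dose | 10 | 0.48 | 52% | 10.0% |
| Optional dose | 4 | 0.19 | 81% | 25.0% |
| Optional dose | 2 | 0.10 | 90% | 50.0% |

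**The case against.** The strongest objection is that the denominator is inferred. The bullet is silent, and the rule comes from a general section that also counts repeated occurrences of an event in a patient only once per treatment phase. Read literally, that rule would keep a patient who reacted to two different injections out of one of the two rows. Section 2.8.1.2 was evidently written for ordinary incidence tables, and a programmer might well depart from it here. That stands as a limit on how sure one can be of what will be printed. It does not remove the gap, because no other rule covers the table.

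The effect is also small where most of the data lie. At scheduled injections, one reaction moves from 4.8% to between 5.0% and 5.9%. This stands.

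The large figures concern optional doses only. The SAP does not say that these get their own rows, and a percentage on a handful of patients is hard to interpret under either denominator. This also stands. The count, which the bullet already requires, is the more useful figure there.

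Finally, the share of all treated patients who react after injection k is a legitimate quantity if it is labelled as such. The plan does not label it so.

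A reader might infer that the table will show a false improvement in tolerance, or that the comparison with placebo is biased. The SAP does not support either as a firm conclusion. It gives no rate of stopping or postponement and no reason to expect the groups to differ in either, and it plans safety as descriptive, without systematic testing (section 2.8).

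**Conclusion.** The point holds as a minor one. Followed as written, the SAP counts patients who never received a given injection as non-reactors to it, and the resulting percentage can only be too low or correct.

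With about 21 patients per group, the relative understatement is about 5% to 19% at late scheduled injections if 20 to 17 patients receive them, and nil if nobody stops. At an optional dose it exceeds 50% if that dose is tabulated and 10 or fewer patients receive it. The recipient counts are assumptions.

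The between-group comparison in a row is distorted only if the proportion of patients receiving that injection differs by group. Numerators, listings, the overall incidence of injection site reactions (for which the safety population is the right denominator) and all pharmacodynamic analyses are unaffected.

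**What to change.** In section 2.8.1.5, state that percentages of injection site reactions by related injection use, as denominator, the safety-population patients in each treatment group who received that injection, and that this number is displayed for each injection. In section 2.8.1.2, except this table from the general denominator rule.

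The cost is a sentence in 2.8.1.5, a short exception in 2.8.1.2 and a changed denominator in one table. The administration records already used for exposure (sections 2.4.1 and 2.11.5) supply the counts.

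Percentages at later injections become slightly less favourable, and those at optional doses will rest on very few patients, which the displayed number makes plain. The change does not remove selection among patients who continue treatment; it only makes the shrinking group visible.

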#### **2.8.1.6 Death and treatment-emergent serious adverse event(s)**

A listing of all deaths (whatever the period: on-study, on-treatment and poststudy) and a listing of all treatment-emergent serious adverse events (SAE) will be presented.

#### **2.8.1.7 Pretreatment adverse events**

A listing of all pretreatment adverse events will be provided.

### **2.8.2 Clinical laboratory evaluations**

#### **Parameters**

The clinical laboratory data consists of blood analysis, including hematology, clinical chemistry serology, and urinalysis. Clinical laboratory values will be analyzed after conversion into standard international units. International units will be used in all listings and tables.

Blood samples for clinical laboratories will be taken at both screening visits, Week 4, Week 8, Week 10 (selected parameters, see below), Week 12/EOT, and for patients who do not enter the OLE, at Week 16 and EOS.

The laboratory parameters will be classified as follows:

- Hematology
  - Red blood cells and platelets and coagulation: hemoglobin, hematocrit, platelet count, prothrombin time, partial thromboplastin time (PTT) at Visit 1 only.
  - White blood cells: total white blood cell count with five-part differential count (neutrophils, eosinophils, basophils, monocytes and lymphocytes), and total red blood cell count.
- Clinical chemistry
  - Metabolism: glucose, total cholesterol, total protein, creatine phosphokinase.
  - Electrolytes: sodium, potassium, chloride, bicarbonate.
  - Renal function: creatinine, blood urea nitrogen, uric acid.
  - Liver function: alanine aminotransferase (ALT), aspartate aminotransferase (AST), alkaline phosphatase, lactate dehydrogenase, total bilirubin (in case of values above the normal range, differentiation in conjugated and non-conjugated bilirubin), albumin.
  - Anti-nuclear antibody (ANA) at Visit 1 for all patients and at Week 10 only for patients who plans to enter the OLE.
  - Anti-ds DNA antibody will be tested if ANA is positive ( $\geq 1:160$  titer).
  - Pregnancy test: serum  $\beta$ -human chorionic gonadotropin will be performed at screening (Visit 1) in women of childbearing potential.
  - Hepatitis and HIV screen: At Visit 1 (screening) and at Week 10 only for patients planned to enter the OLE). Screen includes: hepatitis B surface antigen (HBsAg), hepatitis B surface antibody (HBsAb), hepatitis B core antibody (HBcAb [total and IgM]) and hepatitis C virus antibodies (HCV Ab), HIV screen (Anti-HIV-1 and HIV-2 antibodies). Patients who are Total-HBcAb positive and HBsAg negative at Visit 1 must undergo HBV DNA testing prior to randomization to determine eligibility. In case of results showing HCV Ab positive, HCV RNA testing must be performed prior to randomization to determine eligibility. At Visit 8, the follow-up testing noted above (HBV DNA or HCV RNA) must be done as needed to determine eligibility for the OLE study.

Urine samples will be collected as follows:

- Urinalysis: Performed at both screening visits, Week 12/EOT, and for patients who do not enter the OLE, EOS. Urine dipstick analysis includes specific gravity, pH, glucose,

ketones, blood, protein, nitrate, leukocyte esterase, urobilinogen and bilirubin. A quantitative measurement for glucose, protein, erythrocytes, and leucocytes will be performed in the event that the urine dipstick is positive for any of the above parameters. If the urine dipstick is positive for proteins, a microscopic analysis will be performed.

- A urine dipstick pregnancy test will be performed at Day 1 prior to randomization, Week 4, Week 8, optional Visit 8.1 (Week 12), Week 12/EOT, Week 16, and EOS.

